**Other Exclusion Criteria**

- Prisoners or subjects who are involuntarily incarcerated.
- Subjects who are compulsorily detained for treatment of either a psychiatric or physical (eg, infectious disease) illness.

Eligibility criteria for this study have been carefully considered to ensure the safety of the study subjects and to ensure that the results of the study can be used. It is imperative that subjects fully meet all eligibility criteria.

**4.2.3 Discontinuation of Subjects from Treatment:** Subjects MUST discontinue investigational product for any of the following reasons:

- Withdrawal of informed consent (subject's decision to withdraw for any reason).
- Any clinical adverse event, laboratory abnormality, or intercurrent illness which, in the opinion of the investigator, indicates that continued participation in the study is not in the best interest of the subject.
- Pregnancy: WOCBP will be instructed to contact the investigator or study staff if they suspect they might be pregnant (eg, missed/late menstrual period) at any time during study. Urine pregnancy tests will be performed at each monthly visit as well. The investigator will immediately notify BMS if a study subject becomes pregnant.
- Loss of ability to freely provide consent through imprisonment or involuntary incarceration for treatment of either a psychiatric or physical illness.

All subjects who discontinue should comply with protocol-specified follow-up procedures outlined in Section 6. This will entail monthly visits if subjects discontinue treatment prior to month 6, and then a visit 2 months after withdrawal and an additional visit four months after withdrawal at which safety and efficacy evaluations will be performed the same as the Month 6 visit. The only exception to this is when a subject withdraws consent or loses the ability to consent freely

(ie, is imprisoned or involuntarily incarcerated for the treatment of either a psychiatric or physical illness). If a subject withdraws before completing the study, the reason for withdrawal must be

documented appropriately. The second six months of open label therapy are optional. Patients will be determined to complete the protocol if they complete Month 6 and two follow up visits. Patients will be considered evaluable for the primary endpoint if they complete Month 6. Patients lost to follow up before Month 6 will be considered non-responders.

## **5. Treatments**

### **5.1 Study Treatment: Abatacept:**

**Definition of Investigational Product:** A pharmaceutical form of an active substance or placebo being tested or used as a reference in a clinical study, including products already with a marketing authorization but used or assembled (formulated or packaged) in a way different from the authorized form, or used for an unauthorized indication, or when used to gain further information about the authorized form. In this protocol, the investigational product is abatacept.

**Definition of Non-Investigational Product:** Other medications used in the study as support or escape medication for preventative, diagnostic, or therapeutic reasons as components of a given standard of care. In this protocol, the non-investigational products are optional depomedrol 40-160 mg intramuscular shots given prn (only if needed) at screening, baseline, or at Months 1 and/or 2. No more than 320 mg total may be given before/at Visit 2.

#### **5.1.1 Identification**

Abatacept Injection, 125 mg/Syringe (125 mg/mL), is a sterile solution for SC administration, which contains approximately 126 mg abatacept, 171 mg sucrose, 8 mg Poloxamer 188, 0.28 mg monobasic sodium phosphate, monohydrate, and 0.84 mg dibasic sodium phosphate, anhydrous, in Water for Injection. It is packaged in 1 mL long glass syringe barrel staked with a 29 gauge stainless steel needle and stoppered with a 7.1 mm rubber stopper. The composition of this solution has a ratio of monobasic sodium phosphate, monohydrate, and dibasic sodium phosphate, anhydrous, used to achieve the target pH of 7.2. It appears clear to slightly opalescent, colorless to pale yellow solution, essentially free of particulate matter on visual inspection.

#### **5.1.2 Packaging and Labeling**

Abatacept SC is known to be supplied in a box of 4 syringes with an open-label. We will require abatacept SC and placebo suitable for the unblinded pharmacist to prepare and dispense in syringes appropriate to maintain the blind.

#### **5.1.3 Handling and Dispensing**

The investigational product should be stored in a secure area according to local regulations. At the OMRF we have a locked pharmacy, an experienced clinical trials pharmacy technician who is on site full time, and appropriate storage conditions for a range of investigational products. An inventory will be kept by the unblended pharmacy technician to ensure that the blinded study medication is dispensed only to authorized study personnel (the coordinator) to ensure that it is given only to the appropriate study subjects.

The investigator is responsible for ensuring that the investigational product is stored under the appropriate environmental conditions (temperature, light, and humidity), as described below. This task will be delegated to our well trained pharmacy technician who will be monitored by an outside

pharmacist from the University of Oklahoma to ensure ongoing completeness of inventory, temperature logs, assignment logs, chain of custody documentation, and regulatory records. Abatacept SC formulations (prefilled syringes) and corresponding placebo will be stored under refrigeration (approximately 2 to 8°C) and protected from long-term (more than 24 hours) exposure to light. Temperature logs will ensure stability of temperature and prevention of freezing. Abatacept injection, 125 mg/syringe (125 mg/mL) and placebo for SC administration are ready to use solutions provided in pre-filled siliconized syringes with a 29 gauge needle. Care will be taken when handling the injectable drug products that are used in this protocol. Proper aseptic techniques must be used when preparing and administering sterile parenteral products such as abatacept. Parenteral drug products should be inspected visually for particulate matter prior to administration. If concerns regarding the quality or appearance of the investigational product arise, it will not be dispensed and BMS will be contacted immediately.

## **5.2 Drug Ordering and Accountability**

### **5.2.1 Initial Orders**

The site will request initial shipment with a Drug Request Form. The unblinded pharmacy technician will provide at least weekly reports of inventory use or more frequently if needed to maintain inventory.

### **5.2.2 Re-Supply**

All resupply requests will be initiated by the site by completion of the Drug Request Form.

## **5.3 Method of Assigning Subjects to a Treatment**

There will be no stratification in this protocol. Patients will be randomized 1:1 to treatment or placebo from Month 1-4. At month 3 patients who are flaring or have not improved despite availability of steroid rescue protocols will be allowed to choose open label Abatacept from Month 4 onwards, however they will be considered non responders at Month 6. From Month 6 onwards, all patients will receive the option to continue in the study and open label Abatacept until Month 12. Patients will continue to be followed Monthly until Month 12 with follow up visits at Months 14 and 16.

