## PROTOCOL SYNOPSIS

Protocol Title:	Clarification of Abatacept Effects in SLE with Integrated Biologic and Clinical Approaches (The ABC Study) The ABC Study:
Site Numbers/ Names:	Site 1: Oklahoma Medical Research Foundation
Research Hypothesis:	Abatacept is effective in lupus arthritis and this will be discernible in a small trial with robust endpoints which incorporates withdrawal of background immune suppressants
Study Schema: Drugs / Doses / Length of Treatment)	
 
1. Abatacept or placebo will be given in a 1:1 randomization subcutaneously q week for six months. Patients may elect to continue six more months on open label Abatacept.
 
2. Background Immune Suppressants will be withdrawn at any time between screening and the first dosing visit.
 
3. At or after screening, patients may elect 40-160 mg depomedrol shots prn not to exceed 320 mg total up to and including the Month 2 Visit (two months after the first dosing visit)
 
4. Additional steroids or immune suppressants, if necessary, will be allowed but the patient will be considered a non-responder on that basis
 
5. At the 3 month visit patients with significant clinical flare unresponsive to optional per protocol treatments may elect to receive open label Abatacept but will be considered non-responders in the primary endpoint at six months.
 

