Subjects will be encouraged to avoid off protocol medications if possible, but if off protocol medications are given, the patient may, at the discretion of the investigator continue in the protocol as a designated “non-responder”, and continue to be followed at monthly visits until the subjects reaches Month 6. Furthermore, patients may elect to receive open label abatacept as early as Month 3 (three Months after the first Dosing Visit) if their disease activity is not improved at that visit compared to baseline. Such subjects will also be designated as non-responders for the primary endpoint at Month 6. For those patients taking daily oral steroids at screening, they will be encouraged to taper these as tolerated if and when they begin to improve. Patients who withdraw from the protocol for any reason will be encouraged to come for safety follow up visits 2 and 4 months after the last study visit.

The primary endpoint will be determined at six months, but all patients can then choose to receive open label abatacept for an additional six months. Maximal duration of treatment will be 12 months. There will be two follow up visits two and four months after the end of study. However, patients who withdraw after six months will be considered completers of the primary study in the amassing of 60 completers. The criteria for evaluation will be improvement (without worsening) in signs, symptoms and diagnostic results as defined by the BICLA (primary endpoint). Additionally joint counts, the SRI 4/5, hybrid SLEDAI, BILAG 2004, CLASI, DIAL, Lupus PRO and SF-36 will be evaluated.

After receiving the first injection in clinic, patients will administer the study medication at home. Subjects will return to the clinic monthly for six months, and those who continue will be evaluated every 4 weeks for the second six months. There will be two follow up visits at two month intervals after the end of study for each patient. Visits at which maximal blood samples are taken due to PD scheduling are Screening, and Months 3, 6, 9 and 12 (up to 160 cc). At all other visits no more than 80 cc maximally can be drawn.

Please refer to the Time and Events Schedule for a grid of procedures.

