### **6.4.1 Primary Efficacy Assessment: BICLA Response**

BICLA stands for BILAG-based Combined Lupus Assessment. The BILAG refers to the British Isles Lupus Assessment Group Index. We will be using the version known as BILAG 2004 (37). This consists of 97 descriptors for signs and symptoms of lupus divided into 9 organ systems (see appendices for case report forms). Each organ system receives a rating of A (severe disease activity), B (moderate disease activity) C (mild disease activity) D (no disease activity in an organ previously affected) or E (organ inactive and never previously active). These ratings are derived from assessments made on each descriptor within each organ and the determination of whether activity is not present, improving, same, worsening or new/recurrent when comparing the degree of disease activity during the past month to the previous month.

The BICLA (8) includes scores from the BILAG, the SLEDAI and the PGA. The SLEDAI which will be used is the hybrid SLEDAI which incorporates components of two SLEDAI versions, the SLEDAI 2K and the SELENA SLEDAI which was devised for the Safety of Estrogens in Lupus Erythematosus

National Assessment (SELENA) trial. The PGA refers to Physician's Global Assessment which is performed on a weighted 100 mm scale devised specifically for lupus designed as part of the SLEFI (SELENA SLEDAI flare index). Based on the BILAG scores at entry (A-E in each organ) the BICLA response is defined by at least one letter grade improvement in each organ without an increase in the SLEDAI score or an increase of 10% in the PGA. There must also be no off-protocol treatment in order to meet this response criteria. The primary endpoint is BICLA response rates at month 6 in the abatacept treatment group vs the placebo group. BICLA response at each month will also be assessed as a secondary endpoint.

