## **6.4.2 Secondary Efficacy Assessments**

***All of the individual components of the BICLA will be assessed in different ways as secondary endpoints. These will include:***

1. BICLA response at each month
2. SRI 4 and 5: Response is defined at an endpoint date (EOS and each month vs baseline) The SRI endpoint (7) is defined as a 4 (or 5) point drop in SLEDAI compared to baseline without an increase in BILAG or 10% worsening by PGA.
3. Tender and swollen joint counts (to be analyzed separately and as composite score)
4. Change in SLEDAI scores (EOS and each month vs baseline)
5. Change in PGA scores (EOS and each month vs baseline)
6. Change in BILAG numerical scores (Addition of organ scores where each A=12, B=8, C=1 and D or E=0).
7. Musculoskeletal BILAG response (% with one grade drop and % who reach C or lower)
8. Responder Analysis using the primary endpoint and assessing baseline evidence of (and changes in) a panel of markers selected to identify high levels of IL6/TH17 signalling, and/or B Cell signaling (Erk/Blys). All methods proposed have been previously standardized and are currently available in our laboratory as reviewed above. These will be re-standardized for the current study.

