## 9. Statistical Considerations

**Enrollment is expected to include at least 70 screened and 60 randomized subjects** subjects have either reached a six month endpoint and/or been defined as a permanent non-responder for off protocol treatment or by dropping out of the protocol.

**The primary endpoint is the proportion of placebo vs treatment subjects who meet the primary endpoint of BICLA response using Chi Square analysis at month 6 as determined by an intent to treat analysis**

Subjects who drop out prematurely for any reason or are treated with off protocol medications or cross over to open label for lack of response at Month 3-6 are considered non responders at month 6.

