#### **9.4.3 Efficacy Analysis**

**Primary Endpoint:** The primary analysis upon which this study is powered will be a two by two analysis of response rates to BICLA endpoint in treatment vs placebo group.

**Exploratory Analysis of Primary Endpoint:** To address potential confounders in a small study a propensity score will be applied to simplify multiple variables into one variable.

**Analysis of Secondary Clinical Endpoints:** include the BICLA and SRI response performed at each month using a Chi Square approach as well as mean SLEDAI, BILAG, CLASI, PGA, DIAL and PRO by paired T test comparing baseline to endpoint (EOS or each month) in placebo patients and separately in abatacept treated patients.

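### Open-label abatacept can start before Month 6, but the plan does not say how later values enter SRI, monthly BICLA, the paired t-tests or the Month 9 biologic comparison

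*Combined protocol and SAP*

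**What the plan says.** **Who may switch, and when.** The option is open to both blinded arms. The Synopsis places it at the Month 3 visit and Section 4.1 allows it as early as Month 3. Section 5.3 says patients flaring or not improved at Month 3 "will be allowed to choose open label Abatacept from Month 4 onwards, however they will be considered non responders at Month 6". Section 9 refers to Months 3-6.

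**What happens to switchers in the analysis.** The Synopsis says they "may elect to receive open label Abatacept but will be considered non-responders in the primary endpoint at six months". Section 4.1 agrees: "Such subjects will also be designated as non-responders for the primary endpoint at Month 6". Sections 5.3 and 9 do not name an endpoint; in Section 9, patients who "cross over to open label for lack of response at Month 3-6 are considered non responders at month 6".

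**Secondary responder endpoints.** Section 9.4.3 says the secondary analyses "include the BICLA and SRI response performed at each month using a Chi Square approach". Section 6.4.2 says SRI "is defined as a 4 (or 5) point drop in SLEDAI compared to baseline without an increase in BILAG or 10% worsening by PGA", with no treatment condition. For BICLA, Section 6.4.1 adds: "There must also be no off-protocol treatment in order to meet this response criteria".

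**Continuous endpoints.** Mean SLEDAI, BILAG, CLASI, PGA, DIAL and patient-reported scores are tested "by paired T test comparing baseline to endpoint (EOS or each month) in placebo patients and separately in abatacept treated patients" (Section 9.4.3).

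**Biologic samples.** Section 6.4.2 (Primary Biologic Endpoint) takes a Month 3 sample before non-responders start new immune suppressants. It repeats sampling at Month 9, in part to capture changes in placebo patients who by then have had three months of abatacept.

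**The concern.** The trial has a clear rule for switchers at its primary endpoint and none that plainly reaches the other endpoints. SRI is a planned between-arm comparison. If post-switch values are used as observed, a placebo patient who fails, moves to abatacept and improves is credited to placebo, and the comparison understates any benefit.

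A non-responder rule cannot act on a mean score. The late paired t-tests in the placebo group may therefore include values recorded on abatacept, and the plan does not say whether its group labels mean as randomised or as treated. Since each test is run within one arm, none of them compares the arms.

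Switching is foreseeable. Background immune suppressants are withdrawn, permitted depomedrol ends at Month 2, placebo BICLA response is planned at about 5%, and the Synopsis lists early crossover among the features that should attract patients. If the rule is left open until after unblinding, it can be chosen with the results in view.

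**Working it through.** **1. Which rule reaches which endpoint**

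| Endpoint and visit | Rule for values after an open-label start |
|---|---|
| BICLA, Month 6 (primary) | Non-responder, stated throughout |
| SRI, Month 6 | Not covered on the Synopsis and Section 4.1 wording; arguably covered by Sections 5.3 and 9 |
| BICLA, Months 4-5 | Depends on whether open-label abatacept is off-protocol treatment |
| SRI, Months 4-5 | None |
| Continuous scores after Month 3 | None |

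On the BICLA row, Section 4.1 words the condition as no off-protocol immune suppressants or steroids, whereas open-label abatacept is offered by the protocol. Section 9 lists crossover separately from off-protocol medication. Section 5.6.1 says non-responder status may carry forward, but only for newly started immune suppressants. The matter stays open.

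**2. Can a switch produce an SRI response?** Entry requires at least 3 tender and 3 swollen joints (Section 4.2.1). The SLEDAI arthritis item needs more than 2 inflamed joints and scores 4 (Appendix 1). Its resolution can supply the 4-point drop for SRI-4, provided the arthritis is absent over the 28-day window and the BILAG and PGA conditions hold. It cannot supply SRI-5 alone.

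**3. The plan's own power figure.** For 40% vs 5% with 60 patients and alpha 0.05, the Section 9.2 table gives 0.86. The continuity-corrected normal approximation with 30 per arm, two-sided, gives 0.859, which reproduces it. The uncorrected Pearson chi-square, by exact enumeration of two binomials, gives 0.943. The illustration below uses the uncorrected test, so its baseline is 0.94.

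**4. Illustration for SRI.** From the plan: 40%, 5%, 30 per arm. These are BICLA planning rates; no placebo SRI rate is given. Assumed: a share f = 0.30 of placebo patients switch, they would be non-responders without the drug, and they respond at a fraction g = 0.5 to 1 of the abatacept rate.

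- Placebo rate as observed = 0.05 + f × g × 0.40 = 0.05 + 0.06 to 0.05 + 0.12 = 11% to 17%.
- Case A, only the placebo rate moves: 40% vs 11% gives 0.76; 40% vs 17% gives 0.51.
- Case B, half as many abatacept-arm patients switch (0.15) and are also counted as observed: abatacept rate = 0.40 + 0.15 × g × 0.40 = 43% to 46%. Then 43% vs 11% gives 0.83; 46% vs 17% gives 0.69.

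In Case B, 40% is the abatacept rate under the non-responder rule. If 40% is instead the as-observed rate, the rule would lower it to 0.40 - 0.15 × g × 0.40 = 37% to 34%. Power under the rule would be 0.91 to 0.86, compared with 0.76 to 0.51 as observed.

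**5. Exposure at Month 9.** Months on abatacept = 9 - start month. A start at Month 3, 4, 5 or 6 gives 6, 5, 4 or 3 months. Only the Month 6 start matches the description.

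**The case against.** The strongest reply is that this is an unstated choice rather than an error. Section 9 specifies intent to treat, although for the primary endpoint, so as randomised is the natural reading of the group labels in Section 9.4.3. As-randomised observed values are a legitimate estimand. That stands for the continuous endpoints: what is missing is a named choice. For SRI the gap goes further, because the trial's principle that a switch means non-response is not carried into a between-arm test of the same kind.

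The power illustration is also open to challenge. Moving only the placebo rate overstates the loss if abatacept-arm switchers also improve and are counted as observed. The rates are borrowed from BICLA. The upper case has patients who failed for three months reach the full six-month response after two or three months of drug, although Section 1.3.2 puts steady state without an IV load at 6 to 8 weeks. All of this stands, which is why both cases are shown and neither is an estimate.

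Three stronger inferences should be resisted:

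- A reader might conclude that SRI-4 is easily reached after a switch. The 28-day window and the BILAG and PGA conditions make it possible, not easy.
- A reader might add patients with no abatacept at Month 9, because open label is optional. The Time and Events Schedule has no pharmacodynamic sampling in its post-treatment follow-up column, so this group is probably empty.
- A reader might take the Month 9 text as claiming uniform exposure. It names one purpose of the sample and does not say that every former placebo patient will have had three months.

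**Conclusion.** The concern holds as an omission in the secondary analyses. As written, a placebo patient's improvement on open-label abatacept can be credited to placebo in the SRI comparison at Months 4 and 5, and at Month 6 on the narrower wording. BICLA at Months 4 and 5 is ambiguous. Late paired t-tests may mix treatments, and the Month 9 description fits only a Month 6 start.

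The documents give no switching rate, so the true size cannot be stated. With 30% of placebo patients switching, chi-square power falls from 0.94 to between 0.83 and 0.51, depending on whether abatacept-arm switchers also count and on how well switchers respond. That range depends on the borrowed rates and the assumed switching.

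A reader might infer that the primary result is at risk. The documents do not support this: Month 6 BICLA has an explicit non-responder rule for switchers, so the primary endpoint and its power are unaffected. The Month 3 biologic sample is unaffected too. The point should be settled before unblinding, but it does not undermine the trial's main conclusion.

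**What to change.** 1. Apply the existing non-responder rule to SRI and monthly BICLA at every visit after an open-label start, identically in both arms. Report as-observed values as a sensitivity analysis.
2. Compare the continuous endpoints between arms, as randomised, at Month 3 and Month 6. Month 3 precedes any open-label dose, but is one month after the last permitted depomedrol, which should be noted. Name the post-switch handling for Month 6 in advance, the same in both arms.
3. Group Month 9 biologic samples from former placebo patients by actual months since the first abatacept dose. Keep the three-month description for Month 6 starters.
4. Reconcile Section 5.3 with the Synopsis, Section 4.1 and Section 9 on when open label may start.

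The cost is a few sentences of analysis wording. No visits, samples or assays are added: Month 3 efficacy data and Month 9 samples are already scheduled, and dispensing records should date the first open-label dose. Two drawbacks should be acknowledged. The non-responder rule can also lower the abatacept rate, and any post-switch rule for continuous scores is a choice of estimand that has to be defended.
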